## **Characterization of DMH Engagement**

This data will be used to characterize patterns of DMH engagement, consumer engagement characteristics and behavior that predict time to disengagement. During this phase, we will periodically review our findings (in samples of approximately 25,000 consumers), to determine if new information is needed to help build predictive models. For instance, we may find that consumers engage in DMH in ways we did not anticipate. To better understand these unanticipated patterns of behavior, we will work with MHA and TS focus groups to rapidly identify what information is needed, and the most efficient way to obtain that information. This is a process that is very common for marketing and R&D research at MHA and TS. (See below for more information on Phase 1 focus groups.)

Non-engagers are consumers who visit MHA and TS websites once and do not return.

- Pre-intenders are those who complete screens on both websites: at MHA pre-intenders will also be those who read and spend time on informational pages (e.g., "Will This Feeling Last Forever?") and at TS be those who begin exploring the TS app but have not moved onto using the app.
- Intenders are those who spend time in self-directed readings, videos and other self-directed materials aimed at reviewing different types of treatment, or motivational readings (MHA) and who complete an initial intake with a TS therapist.
- Actors are those who start treatment with a TS therapist and engagement/disengagement will be measured over the course of days and weeks.
- Cyclers are those who return to MHA screenings and materials and those who stop and restart treatment at TS.

Transition between phases will be measured by consumer behavior change in meta-data. For instance, transition from pre-intender to intender may be modeled by a consumer who completed an MHA screen and then clicked through to pages or tools covering information about mental health. Transition from intender to actor maybe modeled by downloading the TS app and beginning a chat with a therapist. Transition from actor to cycler will be measured by number of returns to TS after initiating treatment. Although we will use these constructs to initially define theory-driven engagement patterns, we will also use these meta-data to explore whether unanticipated engagement patterns exist.

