Digital mental health (DMH) is the use of technology to improve population well-being through rapid disease detection, outcome measurement, and care. DMH is a rapidly evolving sector, and it is estimated that the market share will reach \$509.2 billion by 2025. Several randomized clinical trials have demonstrated that DMH tools are highly effective and capable of incredible reach with impressive return on investment. However, most consumers do not fully engage; the average length of engagement is only 2-4 weeks, with most consumers discontinuing use within hours of downloading. Studies on the impact that limited DMH engagement has on consumer outcomes are mixed. For instance, our work found that DMH engagement may be cyclical, with consumers engaging in short bursts over time, depending on current needs and goals. Research on the relationship between engagement and outcomes is mixed, indicating the study of engagement is incomplete without careful tracking of DMH's impact on improving mental well-being. Thus, the field currently lacks an understanding of DMH engagement patterns and which practices are effective at sustaining engagement or re-engaging users who are likely to benefit. In this partnership among Mental Health America (MHA), Talkspace (TS) and the University of Washington (UW), we aim to study 1) how consumer engagement in DMH varies, 2) the association between engagement and positive outcomes, and 3) the effectiveness of personalized strategies for optimal engagement with DMH treatment. We leverage established theories of health behavior change and the use of DMH to achieve health goals (the Health Action Process Approach and the Lived Informatics Model). This study will prospectively follow a very large, naturalistic sample of MHA and TS consumers, and will apply micro-randomized trials to address the following aims:

**AIM 1**: To characterize patterns of DMH engagement, the proportion of DMH consumers who fall into different engagement categories, and the outcomes associated with different engagement categories.

H1a: Engagement longevity, content, and selected DMH services will vary across baseline characteristics (symptom severity, stated goals, demographics).

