**AIM 3b.** Using a SMART designed trial of 10,000 TS consumers, of which 250 will participate in a survey after they discontinue treatment for two weeks, we will compare effective engagement strategies tailored to subtypes developed under Aim 2 to study the mediated impact of engagement strategies on consumer mental health outcomes (e.g. PHQ9). This activity will occur in Y04 of the partnership. We will prospectively recruit participants into micro-randomized and SMART trials to collect additional survey information on participants about self-efficacy (task, coping and recovery), perceived risk/needs, planning skills and anticipated outcomes. We will determine if engagement strategies targeted to consumer engagement subtype will enhance engagement and in turn result in improved clinical outcomes. These will be compared to generic strategies that are not subtype targeted.

Update August 2023: Talkspace will no longer be involved for year 4 of the project and will not complete activities for aim 3B. All aim 3B activities will occur with MHA, broken down into two parts: (1) a Sequential Multiple Assignment Randomized Trial (SMART) of a projected 50,000+ participants and (2) a DIY tool longitudinal randomized control trial (RCT). This is possible with no change in our aim purpose or final budget.

(1.6) Study design. Provide a one-sentence description of the general study design and/or type of methodology.

Your answer will help HSD in assigning applications to reviewers and in managing workload. Examples: a longitudinal observational study; a double-blind, placebo-controlled randomized study; ethnographic interviews; web scraping from a convenience sample of blogs; medical record review; coordinating center for a multi-site study.

This is a prospective, longitudinal and iterative study, divided into three phases:

Phase 1: Data analysis of existing data from 100,000 MHA and TS of data collected between 2020 and the end of Y01 of the project.

Phase 2: Building off findings from Phase 2, rapid and iterative micro-trials (MRTs) of engagement strategies Phase 3: a culminating sequential multiple assignment randomized trial (SMART) used to optimize match between client subtypes identified in Phase 2 and engagement strategies identified in Phase 1.

This initial IRB application is for Phase 1 activities only. Subsequent modifications will be submitted for Phase 2 and Phase 3 once appropriate.

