# **4 RECRUITING and SCREENING PARTICIPANTS**

Confirmed

**4.1** Recruiting and Screening. Describe how subjects will be identified, recruited, and screened. Include information about: how, when, where, and in what setting. Identify who (by position or role, not name) will approach and recruit subjects, and who will screen them for eligibility.

## Phase 1

Phase 1 Data Analysis: Participants will not be actively recruited into this phase of the study. Participants will be all consumers who naturalistically engaged with MHA and/or TS over the past 2 years (2018-2020) and who naturalistically engage during the study. Both MHA and TS, as part of routine practice and as part of their terms and conditions, explain to consumers that their information may be used for research purposes and shared with researchers in academic settings to better understand mental illness and for quality improvement purposes.

Phase 1 Focus Groups: Potential participants will be randomly selected from MHA and TS consumers who will receive an invitation to participate in the focus groups.

Phase 1 Talkspace Survey: Potential participants will be TS consumers who choose to respond to invitations received in-app, by email, or as a push notification. This method of recruitment follows procedures used by TS marketing for non-study related surveys.

## Phase 2

Phase 2 MRTs: Participants will not be actively recruited into this phase of the study. Participants will be consumers who naturalistically engage with MHA and/or TS during this phase. Both MHA and TS, as part of routine practice and as part of their terms and conditions, explain to consumers that their information may be used for research purposes and shared with researchers in academic settings to better understand mental illness and for quality improvement purposes.

Phase 2 Focus Groups: Potential participants will be randomly selected from MHA and TS consumers who will receive an invitation to participate in the focus groups.

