# **5 PROCEDURES**

**5.1 Study procedures**. Using lay language, provide a complete description of the study procedures, including the sequence, intervention or manipulation (if any), drug dosing information (if any), blood volumes and frequency of draws (if any), use of records, time required, and setting/location. If it is available: Upload a study flow sheet or table to **Zipline**.

For studies comparing standards of care: It is important to accurately identify the research procedures. See UW IRB POLICY:
Risks of Harm from Standard Care and the draft guidance from the federal Office of Human Research Protections, "Guidance on Disclosing Reasonably Foreseeable Risks in Research Evaluating Standards of Care"; October 20, 2014.
Information about pediatric blood volume and frequency of draws that would qualify for expedited review can be found in this reference table on the Seattle Children's IRB website.

#### Phase 1

**Phase 1** will consist of analysis of existing data curated from the beginning of 2020 (prior to award) and to the end of Y01, for a total of 100,000 consumers. Data include meta-data collected from MHA and TS websites as well as surveys and screens routinely collected at MHA and TS for marketing and QI purposes.

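### The Aim 1 cycler share depends on when people entered, because return is judged up to the data cut with no common observation period or censoring rule

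*Protocol*

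**What the plan says.** **Categories.** Protocol section 5.1, Characterization of DMH Engagement, uses return to define two of its five categories: "Non-engagers are consumers who visit MHA and TS websites once and do not return" and "Cyclers are those who return to MHA screenings and materials and those who stop and restart treatment at TS". Neither definition has a time limit. Pre-intenders, intenders and actors are defined by what the person has done (screens, materials, intake, treatment). H1b in section 1.5 defines non-engagers differently, as visitors who use no services, and does not mention return.

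**Data window.** Section 5.1 describes "existing data curated from the beginning of 2020 (prior to award) and to the end of Y01, for a total of 100,000 consumers". Section 1.6 agrees: "data collected between 2020 and the end of Y01 of the project". Section 4.1 includes people who engaged "over the past 2 years (2018-2020) and who naturalistically engage during the study". Section 6.1, on minors, runs the data from 2018 to the project's final year.

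**Expected pattern.** Section 1.5 reports that "DMH engagement may be cyclical, with consumers engaging in short bursts over time". It gives no gap length.

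**Interim looks.** Section 5.1 says "we will periodically review our findings (in samples of approximately 25,000 consumers") to decide whether more information is needed. It does not say how those samples are drawn.

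**What is absent.** I found no return window, minimum follow-up, last entry date or censoring rule for return in either document. The SAP covers Aim 3B only.

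**The concern.** Whether someone has ever returned can only be judged over the time they were observed. With continuous entry and a calendar end to the data, that time runs from nearly the whole window down to almost none. The protocol itself expects gaps between bursts of use, so some people who will return have not yet done so at the cut. The rule then leaves them in whichever category they had reached.

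This matters for two reasons:

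- The proportion of consumers in each category is a stated target of Aim 1. Incomplete observation can only hide returns, so the direction of the error is fixed.
- The error is concentrated in late entrants. Anything that drifted over the window (site content, services offered, mix of users) can then look like a predictor of cycling. Aim 2 takes the Aim 1 engagement patterns as an input to its subtypes.

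**Working it through.** There is no plan figure to reproduce. The 100,000 is a volume count with no follow-up time behind it, so the check asks how large the loss could be under stated assumptions.

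**Inputs**

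- From the protocol: return decides the label; entry is continuous; data end at the end of project year 1. A single cut is the natural reading of sections 1.6 and 5.1.
- Assumed: entry is uniform over *T* months. For someone who will eventually return, time from entry to first qualifying return is exponential with mean *m* = 1, 3 or 6 months.
- Choice of *T*: a window that opens before the award and runs through a full award year is longer than 12 months. I use 21 months, since the end date of year 1 is not given, and 36 months to represent the longer windows in sections 4.1 and 6.1.

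**Share of eventual returners missed.** A person followed for *f* months has not yet returned with probability exp(−*f*/*m*). Averaging over *f* uniform on 0 to *T* gives (*m*/*T*)(1 − exp(−*T*/*m*)).

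| | *m* = 1 | *m* = 3 | *m* = 6 |
|---|---|---|---|
| *T* = 21 | (1/21)(1 − e^−21) = 4.8% | (3/21)(1 − e^−7) = 14.3% | (6/21)(1 − e^−3.5) = 27.7% |
| *T* = 36 | (1/36)(1 − e^−36) = 2.8% | (3/36)(1 − e^−12) = 8.3% | (6/36)(1 − e^−6) = 16.6% |

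**Dependence on entry date.** For entrants in the last *k* months, put *k* in place of *T*. For entrants in the first month of a 21-month window, the missed share is *m*(exp(−20/*m*) − exp(−21/*m*)).

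| Entered | *m* = 1 | *m* = 3 | *m* = 6 |
|---|---|---|---|
| First month of 21 | 0.0% | 0.1% | 3.3% |
| Last 3 months | 31.7% | 63.2% | 78.7% |
| Last month | 63.2% | 85.0% | 92.1% |

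**Effect on a proportion.** Take an assumed true cycler share of 30% and *m* = 3. It would be reported as 0.30 × (1 − 0.143) = 25.7% for *T* = 21, or 0.30 × (1 − 0.083) = 27.5% for *T* = 36.

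**What a fixed window does.** If everyone is judged over the same *W* months after first visit, the missed share is exp(−*W*/*m*) whatever the entry date.

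| | *m* = 1 | *m* = 3 | *m* = 6 |
|---|---|---|---|
| *W* = 3 | 5.0% | 36.8% | 60.7% |
| *W* = 6 | 0.2% | 13.5% | 36.8% |

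A fixed window therefore removes the dependence on entry date but not the undercount of eventual returners. With *W* = 3 and *m* = 3, the 30% example becomes 0.30 × (1 − 0.368) = 19.0%, lower than under the rule as written.

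**Talkspace.** A Talkspace user must stop before restarting, so the time to qualify includes time in treatment. Section 1.8b reports 40% not engaging for 3 weeks, 21% not beyond 6 and another 12% not past 9. Read as additive, which is my assumption, 100 − 40 − 21 − 12 = 27% are still engaged after nine weeks and cannot yet count as cyclers.

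**The case against.** - **The receiving category.** A reader might infer that late entrants who would cycle back are all counted as non-engagers. The documents do not support this. Under section 5.1, a one-visit person who completed a screen fits pre-intender, one who used self-directed materials fits intender, and a Talkspace patient in treatment is an actor. Under H1b, non-engagement is not about return at all. The loss from the cycler group stands, but where those people land varies.
- **The size rests on assumptions.** This stands. Uniform entry, exponential gaps, the means and the 30% share have no source in the documents. If returns come within about a month, the loss is 5% or less for a 21-month window. The protocol also does not say how the 100,000 are drawn from the window.
- **Downstream reach.** A reader might infer that the Aim 3 trials are compromised. The Aim 3B Study 1 conditions are tailored on demographics, severity, perceived need and stated intention, and are randomised; they do not use these labels. Section 5.1 also treats the categories as a starting point and looks for unanticipated patterns. The route into Aim 2 remains.
- **The reviews of about 25,000.** They serve only to decide whether more information is needed, and their sampling is not described, so the effect there is conditional.
- **Level of detail.** This is a lay-language ethics form, and timing data such as time between logins will be collected. But the category rule is stated, and followed as written it gives proportions that depend on entry date. The planned look at predictors of time to disengagement concerns leaving, not returning.

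**Conclusion.** The concern holds. The cycler definition has no common observation period, entry continues up to the cut, and nothing accounts for unequal follow-up. The Aim 1 cycler share is therefore biased down and the categories occupied at the cut are biased up. The label varies with entry date, and this can carry into Aim 2. The direction is certain, but the size cannot be derived from the documents. Under the assumptions above it is about 5%, 14% and 28% of eventual returners for 21 months, and 3%, 8% and 17% for 36 months. The randomised Aim 3B comparisons are not directly affected. Two inconsistencies add to the problem and need reconciling: the data window (sections 1.6 and 5.1 against 4.1 and 6.1) and the non-engager definition (section 1.5, H1b, against 5.1).

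**What to change.** 1. **Aim 1 proportion.** Estimate the cumulative incidence of return (MHA) by time since first visit, and of restart (Talkspace) by time since stopping, with stopping defined. Use all entrants, censor at the data cut, and report at stated horizons. This assumes that entry date is unrelated to time to return; show the curves by entry period as a check.
2. **Per-person label for Aim 2 and the 25,000-person reviews.** Define it as *returned within W* for one fixed *W*, and apply it only to people observed for at least *W*.
3. **Dates.** Section 5.1, Identifiability of Data, has dates altered relative to a randomly selected date and does not say whether one date serves everyone. Keep the true time from first visit to the cut for each person.
4. **Reconcile** the stated data windows and the two non-engager definitions.

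**Cost.** Code-book and analysis wording, or a re-tabulation if Phase 1 is complete. The latest entrants drop out of the labelled set but stay in the cumulative-incidence estimate. The label no longer counts later returns: with a 3-month mean gap it misses 37% of eventual returners at *W* = 3 months and 13.5% at *W* = 6. The curve, or a longer *W*, should therefore carry the Aim 1 proportion.

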## **Focus Groups**

#### Phase 1

Focus group participants will be randomly chosen from MHA and TS adult consumers. Focus groups will be recruited at 3 different time points (6 groups, 3 for TS and 3 for MHA). Potential participants will receive an invitation to participate in focus groups. These invitations will be distributed on the platforms (either MHA or TS) using methods that are standard for marketing and R&D research at both MHA and TS (including but not limited to emails, pop-ups, messages from chat bot features, or messages in the participant's inbox on the system). If consumers are interested in learning more, they can respond to the invitation by clicking on a link, which alerts study team members at MHA or TS.

- Talkspace Focus Groups: A member of the study team will reach out to the consumer to provide more information, schedule activities, and provide information on engaging in the focus group (e.g. Zoom info).
- MHA Focus Groups: After viewing/receiving the invitation, consumers complete an interest form to indicate their interest in the focus group. A member of the study team emails interested participants to provide information about the focus group, which is all done online including instruction, options for anonymity, and any recording that may happen.

Participants will first be presented with the study we are conducting, its purpose and then results from initial data analysis on engagement patterns. Participants will be asked their impressions of the data and potential engagement subtypes and patterns that have been identified (e.g. preintender, intender, actor). If from the discussion we determine that more information is needed in the form of a survey to the next cohort of consumers, we will the ask them to help us write and design the survey (which will be submitted to IRB via a modification if needed). If they determine that we do not require more information, we will thank the participants for their time and ask their interest in participating in a future focus group. Focus groups may be audio and video recorded; consent for this audio and videorecording will be provided by participants in order for any recordings to take place, and participants may choose to turn their video off prior to the start of video recording. Focus group participants will receive \$40 for 90-120 minutes of their time.

## Talkspace Nudge Survey

Talkspace nudge survey respondents will be English speaking TS consumers aged 18 and over who has a messaging therapy or messaging + live therapy plan and who choose to respond to invitations received in-app, by email, or as a push notification. The invitations will contain a link to the survey, which has been programmed in Qualtrics hosted by UW. The TS consumers will review the statement that contains all necessary elements of consent and confirm their age. If the consumer indicates that they are younger than 18, the survey will not allow

APPLICATION IRB Protocol

them to continue. Respondents are made aware that their responses to this survey are tied their other information on Talkspace (e.g., the meta-data described above).

The survey asks questions about how receiving communication from Talkspace may change a consumer's use of the services including requesting feedback on language used in different types of communications, frequency of communications, and preferences around communications. Respondents are asked demographic questions (e.g., age, race, ethnicity, education, income, household size, health status, and language) and questions about which device(s) they use Talkspace on. Participants are then given a vignette about a Talkspace user and shown example text for potential push notifications. The exact copy (language, etc.) seen by each participant will be randomized but all respondents will answer the same questions. Examples of the copy that participants will be randomly exposed to have been uploaded to Zipline in the Talkspace site ("Talksapce\_Nudge Survey Copy Options\_MHATS"). They are then asked to respond to questions about how that language may impact their utilization of Talkspace (e.g., would they be more or less likely to message their therapist after seeing that language). Respondents are then asked questions about their preferences related to receiving push notifications (e.g., how often, how many, do they currently receive push notifications from TS) and whether or not seeing a push notification impacts their utilization of TS. We request flexibility in the specific language of both the copy and survey questions; we will submit a modification if any edits go beyond the scope described here. We expect that the survey will take approximately 10 minutes to complete.

## Phase 2

